#### **4.2.3 Outpatient dose titration period**

##### **Visit 3 (Outpatient dose titration period Visit)**

During the outpatient dose titration phase, patients continue to receive sacubitril/valsartan or enalapril. There are 3 available doses of study drug administered twice daily. All subsequent dose changes during the medication titration period is selected using a dose titration algorithm based on systolic blood pressure (SBP) (Figure 1). Clinician-investigators are encouraged to up titrate sacubitril/valsartan to target dose (i.e., dose level 3) as tolerated during the medication titration phase. every attempt should be made to complete the dose titration period within 8 weeks regardless of any down-titration that may occur.

#### **4.2.4 Follow-up period**

##### **Visit 4 (Follow-up Visit)**

Follow-up visits are scheduled for Weeks 4, 12 and 24. Blood and urine samples are sent to a central laboratory for hematology, chemistry, and serum and urinary biomarkers. Professionals use Philips IE33 ultrasound system (Philips Medical System, Bothell, Washington, USA) for echocardiographic measurements. In addition to the protocol-required visits, patients may be seen at any time throughout the study at the discretion of the investigator to investigate or follow any new lab abnormalities or adverse events.

Monitoring of safety and tolerability will include: (1) hyperkalemia; (2) symptomatic hypotension; (3) increase in serum creatinine; (d) angioedema; and (e) adverse events and serious adverse events. If, in the opinion of the investigator, the patient cannot tolerate the target dose of study drug, the investigator should consider whether non-life saving medication (e.g., CCBs, nitrates,  $\alpha$ -blockers) can be reduced to rectify the situation before considering reducing the dose of the study drug to the lower dose level. The dose of background disease modifying drugs, such as  $\beta$ -blockers and mineralocorticoid receptor antagonists, should not be reduced to facilitate maintenance of study drug. If the situation is not rectified despite adjusting/discontinuing nonlife-saving medications or if adjusting non-life-saving concomitant medications is not possible, patients who no longer tolerate the target dose at any time during the course of the trial can be down-titrated to the lower dose level at the investigator's discretion (please refer to Figure 1 for dose levels available for titration). However, every attempt should be made to re-challenge the patients so that they are kept on the maximal tolerated dose of study drug for as long a duration as possible throughout the outpatient

dose titration and follow-up period of the trial. Please refer to Section 6.4.3 for a guidance on study drug dose adjustment.

## 5 Population

### 5.1 Inclusion criteria

Patients eligible for inclusion in this study have to fulfill all of the following criteria:

1. Patients must give written informed consent before any assessment is performed
2. Outpatients  $\geq 18$  years of age, male or female
3. Had typical pain and Diagnosed as acute anterior STEMI according to electrocardiogram, high-sensitivity troponin, and coronary angiography
4. Systolic blood pressure  $\geq 100$ mmHg without symptoms of dizziness during the last 12 hours prior to randomization

### 5.2 Exclusion criteria

1. Previous history of myocardial infarction or chronic heart failure
2. Previous PCI, coronary artery bypass graft (CABG), implantation of other heart assist devices or heart transplantation
3. Known history of angioedema
4. Previous history of intolerance to recommended target doses of ACEIs or ARBs.
5. Previous use of sacubitril/valsartan
6. History of hypersensitivity or contraindications to the study drugs including ACEI, ARB, sacubitril/valsartan
7. Symptomatic hypotension and/or a SBP  $< 100$  mmHg at Visit 1 (screening), Visit 2 (randomization), Visit 3 (outpatient dose titration) or Visit 4 (follow-up)
8. Estimated GFR  $< 30$  mL/min/1.73m^2 as measured by the simplified MDRD formula at Visit 1 (screening), Visit 2 (randomization), Visit 3 (outpatient dose titration) or Visit 4 (follow-up) or  $> 25\%$  decline in eGFR between Visit 1 and Visit 2 or between Visit 2 and Visit 3 or between Visit 3 and Visit 4
10. Serum potassium  $> 5.2$  mmol/L at Visit 1 (screening), Visit 2 (randomization), Visit 3 (outpatient dose titration) or Visit 4 (follow-up)
11. History of severe pulmonary disease
12. Diagnosis of peripartum or chemotherapy induced cardiomyopathy prior to Visit 1
13. Documented untreated ventricular arrhythmia with syncopal episodes within the 3 months prior to Visit 1
14. Symptomatic bradycardia or second or third degree heart block without a pacemaker
15. Presence of hemodynamically significant mitral and/or aortic valve disease, except mitral regurgitation secondary to left ventricular dilatation

16. Presence of other hemodynamically significant obstructive lesions of left ventricular outflow tract, including aortic and sub-aortic stenosis

17. Life expectancy is less than 1 year

18. Any surgical or medical condition which might significantly alter the absorption, distribution, metabolism, or excretion of study drugs, including but not limited to any of the following

- History of active inflammatory bowel disease during the 12 months before Visit 1.
- Current duodenal or gastric ulcers during the 3 months prior to Visit 1
- Evidence of hepatic disease as determined by any one of the following: AST or ALT values exceeding 2 x ULN at Visit 1, history of hepatic encephalopathy, history of esophageal varices, or history of portacaval shunt
- Active treatment with cholestyramine or colestipol resins

19. Pregnant or nursing (lactating) women, where pregnancy is defined as the state of a female after conception and until the termination of gestation, confirmed by a positive hCG laboratory test (> 5 mIU/mL)

20. Women of child-bearing potential, defined as all women physiologically capable of becoming pregnant, including women whose career, lifestyle, or sexual orientation precludes intercourse with a male partner and women whose partners have been sterilized by vasectomy or other means, UNLESS they are using two birth control methods. The two methods can be a double barrier method (if accepted by the local regulatory authority and ethics committee) or a barrier method plus a hormonal method

- Adequate barrier methods of contraception include: diaphragm, condom (by the partner), intrauterine device (copper or hormonal), sponge or spermicide. Hormonal contraceptives include any marketed contraceptive agent that includes an estrogen and/or a progesterone agent.

- Reliable contraception should be maintained throughout the study and for 7 days after study drug discontinuation.

- Women are considered post-menopausal and not of child bearing potential if they have had 12 months of natural (spontaneous) amenorrhea with an appropriate clinical profile (e.g. age appropriate, history of vasomotor symptoms) or six months of spontaneous amenorrhea with serum FSH levels > 40 mIU/mL or have had surgical bilateral oophorectomy (with or without hysterectomy) at least six weeks ago. In the case of oophorectomy alone, only when the reproductive status of the woman has been confirmed by follow up hormone level assessment.

No additional exclusions may be applied by the investigator, in order to ensure that the study population will be representative of all eligible patients.

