### **4.2.2 Randomization**

#### **Visit 2 (Randomization Visit)**

Patients who have met all the inclusion criteria and none of the exclusion criteria at the end of the screening period will be randomized to either enalapril or sacubitril/valsartan in a 1:1 ratio. Patients randomized to enalapril continue to receive enalapril, while

patients randomized to sacubitril/valsartan discontinue enalapril to ensure a minimum 36-hour washout period prior to initiation of ARNi therapy. The first dose of sacubitril/valsartan is followed by 6 hours of monitoring for hypotension. After the condition is stable, patients can be discharged from the hospital at any point in time at the discretion of the clinician-investigator. The starting dose during the in-hospital initiation phase is selected using a dose titration algorithm based on systolic blood pressure (SBP) (Figure 1).

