### **6.4.3 Permitted study drug dose adjustments and interruptions**

Every attempt should be made to maintain patients on the target study drug dose level for as long a duration as possible throughout the trial. If, however, in the opinion of the investigator, the patient does not tolerate the target dose of study drug (dose level 3), the investigator should consider whether non-life saving medication (e.g., CCBs, nitrates,  $\alpha$ -blockers) can be reduced to rectify the situation, before considering to reduce the dose of the study drug to the next lower dose level. If adjustment/elimination of

other non-life-saving HF medications is not possible or does not alleviate the side effects of concern, the investigator may down-titrate the dose of the study drug to the next lower level up to complete withdrawal of the study drug. The patient should be re-challenged with the higher dose when the investigator feels it is appropriate to do so per the directions provided below in this section. If needed, the study drug may be stopped completely, but the patient should continue to attend the study visits and be followed until the completion of the study. Ultimately the goal is to keep the patient on the highest study drug dose possible for as long as possible and to follow the patient in the study as long as possible.

Study drug dose level adjustments should mainly be based on overall safety and tolerability with special focus on a) hyperkalemia; b) symptomatic hypotension; and c) clinically significant decrease in eGFR/increase in serum creatinine (see Appendices 2, 3 and 4 for treatment guidelines for hyperkalemia, management of BP, and renal dysfunction, respectively).

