### **Adjustment of study drug dose level**

#### **Study drug dose adjustments during the dose titration period**

Once the condition is stable, the patient should increase the titration to the next higher dose level every 2 weeks in an attempt to gradually titrate the patient to the target study drug dose level (dose level 3).

At the investigator's discretion, sacubitril/valsartan 200 mg bid can be down-titrated to sacubitril/valsartan 100 mg bid until such time that investigator believes the patient may be able to tolerate titration back up to sacubitril/valsartan 200 mg bid. If the investigator does not feel that the patient will ultimately be able to tolerate this dose, he/she may withdraw the patient from the study without re-challenge. If the tolerability issues are not alleviated despite down-titration by one dose level, the investigator may lower the study drug dose further to the next lower level for 1 to 4 weeks, up to temporary withdrawal of the study drug. Again, once stable, the patient should be re-challenged with up-titration to the next higher dose level every 1 to 4 weeks in an attempt to bring back the patient gradually to the target study drug dose level (dose level 3).

In some instances, according to the safety and tolerability criteria and the investigator's judgment, dose level 1 or 2 could be maintained if he/she considers that the patient's condition would not allow any further up-titration to the target dose of study medication (level 3). In this case it would be acceptable to maintain the patient at dose level 1 or level 2, whichever is the higher and tolerated dose level by the patient.

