## **10 Data analysis**

### **10.1 Populations for analysis**

The full analysis set (FAS) will consist of all randomized patients. Following the intent-to-treat principle, patients will be analyzed according to the treatment to which they were assigned at randomization. Efficacy variables will be analyzed based on the FAS as the primary population.

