### **Two types of response to serum creatinine increase are described:**

#### **Surveillance situation**

If, at any time after randomization, eGFR decreases by  $\geq 25\%$  from baseline (Visit 5) (or if serum creatinine concentration increase to 2.5 mg/dL [221  $\mu\text{mol/L}$ ]), the investigator will check for potentially reversible cases of renal dysfunction such as:

- Non-steroidal anti-Inflammatory drug intake, antibiotics, or other treatments known to affect creatininemia
- Volume decrease
- Urinary infection

- Urinary tract obstruction
- Study medication

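### Exclusion criteria 7, 8 and 10 are written to apply after randomization, contradicting the follow-up rules and the all-randomized analysis set and creating a risk of informative exclusion

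*Protocol*

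**What the plan says.** Protocol 5.2, repeated in the synopsis, lists three criteria that run past randomization:

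- Criterion 7: symptomatic hypotension and/or a systolic pressure below 100 "mmHg at Visit 1 (screening), Visit 2 (randomization), Visit 3 (outpatient dose titration) or Visit 4 (follow-up".
- Criterion 8: eGFR below 30 at any of the same four visits, or a more than 25% "decline in eGFR between Visit 1 and Visit 2 or between Visit 2 and Visit 3 or between Visit 3 and Visit 4".
- Criterion 10: potassium above 5.2 "mmol/L at Visit 1 (screening), Visit 2 (randomization), Visit 3 (outpatient dose titration) or Visit 4 (follow-up".

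Other sections treat eligibility and follow-up differently:

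- 4.2.2: patients meeting all inclusion criteria and "none of the exclusion criteria at the end of the screening period will be randomized".
- 6.4.3 (opening text): if drug is stopped, "the patient should continue to attend the study visits and be followed until the completion of the study". Sections 6.4.6 and 7 say the same in substance.
- Appendix 4, at an eGFR fall of 25% or more after randomization: "the investigator will check for potentially reversible cases of renal dysfunction such as" a list of causes. Appendices 2 and 3 likewise manage raised potassium and symptomatic hypotension in patients who remain in the trial.
- 10.1: "The full analysis set (FAS) will consist of all randomized patients", analysed as assigned.

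Two places do mention removal. During titration, if the investigator doubts that the patient will ever tolerate sacubitril/valsartan 200 mg bid, 6.4.3 says "he/she may withdraw the patient from the study without re-challenge". Appendix 4 withdraws patients for eGFR decline in a randomization period that it does not delimit.

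**The concern.** An exclusion criterion should be decidable before allocation. Here the Visit 3 and Visit 4 limbs, and the last two eGFR windows in criterion 8, can only be met by someone already randomized and on study drug. The triggers are hypotension, renal decline and raised potassium. Section 1 names hypotension, renal insufficiency and hyperkalemia as safety endpoints, and 10.5 lists the same events.

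The protocol never says what happens to a randomized patient who meets one of these criteria at Visit 3 or 4, nor which text prevails. Section 12 permits no authorized deviations, so a site following 5.2 literally could take the patient out. The glossary makes that costly, because after premature withdrawal no further assessments are planned. The later outcome data would then be missing because of how the patient responded to the assigned drug. An all-randomized FAS does not recover measurements that were never taken.

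**Working it through.** **1. Timing.** Randomization is at Visit 2 (4.2.2). At Visit 3 patients are taking study drug (4.2.3), and Table 7-1 places Visit 3 at weeks 2 to 8. The echocardiographic outcomes are measured at weeks 12 and 24 (7.4.5, 10.3.1). A patient removed at Visit 3 would therefore have no week 12 or week 24 LVEF, LVEDV or LVESV.

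**2. The criteria beside the post-randomization guidance.**

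| Trigger | 5.2 (Visits 3 and 4) | Appendices, after randomization |
|---|---|---|
| Potassium | excluded above 5.2 mmol/L | Appendix 2: graded management above 5.3 mmol/L |
| Blood pressure | excluded below 100 mmHg, or if symptomatic | Appendix 3: management of symptomatic hypotension |
| eGFR | excluded at a fall above 25% between visits, or below 30 | Appendix 4: surveillance at a fall of 25% or more from baseline, action at 40% or more |

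The same patient can be excluded under one text and managed in the trial under the other.

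**3. The plan's own sample size (10.6).** Inputs: LVEF difference 3, SD 6 (reading the 3% ± 6% this way), alpha 0.05 taken as two-sided, power 80%, 1:1 allocation. The standardized effect is 3/6 = 0.5. A two-sample t-test needs 63.77, so 64 per arm. For 10% loss, 128/0.9 = 142.2, against the stated 142. The figures reproduce.

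**4. Possible bias (assumptions, not document figures).** Let p1 and p0 be the proportions excluded in the two arms, and let excluded patients have a mean LVEF change k points worse than those who remain. Each arm's remaining mean is then too high by p × k, so with a common k:

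bias = (p1 − p0) × k, in favour of the arm with more exclusions.

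- k = 4, rates 5 points apart: 0.05 × 4 = 0.2 points, or 0.2/3 = 7% of the planned effect.
- k = 4, rates 15 points apart: 0.15 × 4 = 0.6 points, or 0.6/3 = 20%.
- Equal rates and equal deficits: 0.

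Varying k as well, with 71 randomized per arm, SD 6, no true effect and complete-case analysis:

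| Excluded | k | Bias | Type I error |
|---|---|---|---|
| 10% vs 5% | 3 | 0.15 | 5.2% |
| 20% vs 10% | 3 | 0.30 | 5.9% |
| 30% vs 15% | 6 | 0.90 | 12.3% |

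**5. Possible loss of power (assumption).** The 64 per arm is already net of the planned 10% loss. Taking a further 10% or 20% off gives:

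- 64 × 0.9 = 57.6 per arm: power 75.8%.
- 64 × 0.8 = 51.2 per arm: power 70.7%.
- No further loss: power 80.1%.

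Measured from 142/2 = 71 randomized per arm, these cases are total losses of 1 − 57.6/71 = 19% and 1 − 51.2/71 = 28%.

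**The case against.** A reader might infer that patients with on-treatment hypotension, renal decline or hyperkalemia will drop out selectively, vanish from the primary analysis and bias both efficacy and safety. The documents do not support that as a statement of fact.

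- No text says that a randomized patient who meets criterion 7, 8 or 10 at Visit 3 or 4 is removed. Section 4.2.2 settles eligibility earlier, and Table 7-1 (badly extracted, so read with caution) appears to show the eligibility check only at screening and, in brackets, at the next visit. The mandatory reasons for stopping drug in 6.4.6 do not name these criteria.
- The FAS contains everyone randomized, and an eligibility criterion does not redefine it. The danger is missing later data, not removal from the analysis set by definition.
- The triggering safety event would be seen at the visit that triggers exclusion, and 8.2 requires SAE reporting until 30 days after participation stops. Later events, not the first one, are at risk.
- No arm-specific rates are given, and Appendix 4 says either study medication could affect renal function. A difference between arms is possible but not shown.
- If the exclusions fell within the planned 10% loss, power would stay at 80%.
- The withdrawal in 6.4.3 is discretionary. The one in Appendix 4 concerns the randomization period, which Table 7-1 lists apart from titration and follow-up. Neither shows removal at Visits 3 and 4 under 5.2.

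All of this stands, and it makes the bias conditional. It does not remove the contradiction: 5.2 names the later visits explicitly, the synopsis repeats them, and no rule of precedence tells a site to disregard them.

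**Conclusion.** The contradiction is established: three exclusion criteria apply, as written, after randomization and on study drug, against 4.2.2, 6.4.3, 6.4.6, 7, 10.1 and Appendices 2 to 4. The consequence is a risk of informative exclusion that arises only if the criteria are enforced as removal from follow-up or analysis. Its size and direction cannot be derived from the documents. The 0.2 to 0.6 LVEF points rest on an assumed 5 to 15 point difference in exclusion rates and an assumed 4-point deficit. The fall in power to about 76 to 71% assumes losses beyond the planned 10%. Both are illustrations. The point deserves correction because measurements lost in this way cannot be recovered afterwards.

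**What to change.** - In 5.2 and the synopsis, limit criteria 7, 8 and 10 to assessments up to randomization: delete the references to Visits 3 and 4, and in criterion 8 delete the Visit 2 to 3 and Visit 3 to 4 eGFR windows.
- State once that every randomized patient stays in follow-up and in the FAS whether or not study drug is stopped.
- Reconcile the study-withdrawal wording in 6.4.3, and in Appendix 4 for anyone already randomized, with 6.4.6, 7 and 10.1.
- The sponsor must reconcile the differing on-treatment thresholds in 5.2 and Appendices 2 to 4. No view is taken here on which is right.

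The cost is a wording amendment. The 64 per group and 142 in total are unchanged, and no visits are added.

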## 6 Treatment

### 6.1 Investigational drugs

after PCI

南昌大学  
医学

The following study drugs will be provided:

- Enalapril 2.5 mg tablets
- Enalapril 5 mg tablets
- Enalapril 10 mg tablets

### **Randomization, Outpatient dose titration and follow-up**

All eligible patients will be randomized to receive either sacubitril/valsartan or enalapril in addition to optimal AMI therapy, as considered appropriate by the investigator and in accordance with standard therapy guidelines, but with the exception of an ACEI or ARB as this will be replaced by study drug. The use of an ACEI or an ARB in addition to study drug after randomization is strictly prohibited.

The following study drugs will be provided:

- Enalapril 2.5 mg tablets (enalapril dose level 1)
- Sacubitril/Valsartan 50 mg tablets (Sacubitril/Valsartan dose level 1, Sacubitril/Valsartan to match enalapril 2.5 mg film-coated tablets)
- Enalapril 5 mg tablets (enalapril dose level 2)
- Sacubitril/Valsartan 100 mg tablets (Sacubitril/Valsartan dose level 2, Sacubitril/Valsartan to match enalapril 5 mg film-coated tablets)
- Enalapril 10 mg tablets (enalapril dose level 3)
- Sacubitril/Valsartan 200 mg tablets (Sacubitril/Valsartan dose level 3, Sacubitril/Valsartan to match enalapril 10 mg film-coated tablets)

Target doses: Sacubitril/Valsartan 200 mg bid and enalapril 10 mg bid.

## **6.2 Treatment arms**

Patients who are eligible for randomization at Visit 2 will be assigned to one of the following two treatment arms in a 1:1 ratio:

- Sacubitril/Valsartan dose level 1 or 2
- Enalapril dose level 1 or 2

## **6.3 Treatment assignment**

At Visit 2, the researcher or his representative will call the researcher in charge of randomization, enter the patient's patient number, and confirm that the patient is eligible for randomization. The researcher in charge of randomization will assign a random number to the patient, which will be used to connect the patient to the treatment arm.

During the titration of the drug, the researcher will decide whether to increase or decrease the dose of the drug based on the patient's blood test and physical examination. Randomization numbers will be generated using the following procedure to ensure that treatment assignment is unbiased. A patient randomization list will be produced by the researcher provider using a validated system that automates the random assignment of patient numbers to randomization numbers. These randomization numbers are linked

to the different treatment arms, which in turn will be linked to medication. The randomization scheme for patients will be reviewed and approved by a member of the Biostatistics Quality Assurance Group.

